#### 11.1 Adverse Events

#### 11.1.1 Reportable AEs

All AEs that occur after the informed consent is signed and baseline assessments are completed (including run-in) must be recorded on the AE CRF (paper and/or electronic) whether or not related to study agent.

For all unsolicited AEs not meeting the criteria for "Serious Adverse Events", the following caveats will apply:

- a. **AEs in the immediate (up to 14 days) post-vaccination periods:** All unsolicited AEs, including anticipated and unanticipated clinical events, clinically significant laboratory abnormalities, and vaccine-related injection site local reactions (e.g., pain, swelling, erythema, pruritus, induration, warmth, etc.) and vaccine-related systemic side-effects (e.g., headache, oral temperature ≥100 degrees F, nausea, fatigue, dizziness, allergic events, bronchospasm, etc.) will be collected for up to 14 days following vaccine administration (1st, 2nd, and 3rd dose) and reported on AE CRFs.
  - i. Note that clinically significant laboratory abnormalities that *pre-dated* vaccine administration and *remain unchanged* (as per the Site Principal Investigator's judgment) after vaccine-administration should not be reported as AEs

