# Additional Study Visit(s) for completing vaccine series:

Additional Study Visits will be offered to participants whose medical schedules did not permit them to complete their vaccine series earlier in the study.

**Study Measurements.** All visits discussed above, except the 13 Month Post-Transplant Visit and Additional Study Visits will, include the following study measurements. The 13 Month Post-Transplant Visit will include a blood draw only, and Additional Study Visits will only include administering the remaining vaccine doses to complete the series.

- History and physical exam
- Blood specimen for measurement of the primary and secondary endpoints
- Collection of cervical/vaginal and oral samples for HPV DNA testing
- Optional collection of urine for HPV DNA testing.
- Optional collection of eyebrow hair samples for future viral DNA testing.
- Optional collection of male genital samples for future HPV DNA testing.
- Baseline and follow-up questionnaires.

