## 7. CLINICAL EVALUATIONS AND PROCEDURES

#### 7.1 Schedule of Events

Study Procedures	Consent and Screen- ing Visit	Pre- Trans- plant Vaccine Visit 1 	Pre- Trans- plant Vaccine Visits 2 and 3 	Trans- plant Surgery	6 Month Post- Trans- plant Visit 	Month Post- Trans- plant Visit 	13 Month Post- Trans- plant Visit 	Add- itional Study Visit(s) 
Assess eligibility	X	X						
Informed consent form and HIPAA authorization	X							
Pregnancy test 	X					X8		
Enrollment		X						
Demographics (race, ethnicity, education)		X						
Review medical history, medications, and laboratory test results		X	X		X	X		
Symptoms assessment and ECOG performance status		X	X		X	X		

Protocol Version 3.11, April 20, 2023

						Proto	coi version 3.	11, April 20, 2
Physical exam including vital signs and weight		X	X		X	X		
Gardasil® 9 HPV vaccination		X	X			X8		X
Collect blood specimen for research		X 	X 	X 	X 	X 	X 	
Self-collection of cervical/vaginal, and oral samples for HPV DNA		X	X		X	X		
Self-collection of urine samples for HPV DNA (optional) 		X	X		X	X		
Collection of eyebrow hairs for future viral DNA testing (optional) 		X	X		X	X		
Self-collection of male genital samples for future HPV DNA testing (optional) 		X	X		X	X		
Interviewer-administered risk factor questionnaire 		X	X		X	X		
Review eligibility criteria	X	X						
Assess adverse events 		X	X			X		
Telephone contact 	X	X	X		X	X		X

<sup>1 Pre-Transplant Vaccine Visit 1 may occur the same day as the Consent and Screening Visit, and will be scheduled ≥30 days prior to the planned transplant surgery.

- Pre-Transplant Vaccine Visit 2 should occur ≥30 days after Pre-Transplant Vaccine Visit 1.
- Pre-Transplant Vaccine Visit 3 should occur ≥3 months after Pre-Transplant Vaccine Visit 2, and ≥5 months after Pre-Transplant Vaccine Visit 1.

- Participants who received only one dose of the vaccine prior to transplant will receive the second dose of the vaccine at this visit.
- Participants who received two vaccine doses prior to transplant will receive the third dose of the vaccine at this visit.
- Participants who received three vaccine doses prior to transplant will not receive a third dose of the vaccine at this visit.

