# **Telephone Calls**

Research staff will contact study participants by phone 24-72 hours after receiving each vaccine dose throughout the study, including pre-transplant vaccines, post-transplant vaccines, and Additional Study Visit(s). Research staff will ask the participant about potential side effects of the immunization. If the participant reports adverse symptoms there will be a follow-up call on day  $7 \pm 2$  days to assess resolution. Participants will also be contacted 5-7 days before each study visit to confirm the appointment. Contact can be made using site standard procedures and/or mechanisms (i.e. automated or manual phone call, text message, or email) .

The following information with be collected during the telephone calls:

- Concomitant medication review
- Adverse events. Participants will be asked if they have experienced any of the following symptoms to assess adverse events:
  - o Pain, swelling, redness, or itching at the vaccine injection site
  - Headache
  - o Fever
  - o Nausea
  - Signs of a severe allergic reaction: hives, a fast heartbeat, dizziness, weakness, difficulty breathing, or swelling of the face and throat
- Additional symptoms experienced by participants will be recorded to assess adverse events

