#### 7.7 Methods for Clinical Procedures

Administration of Vaccine. The CDC HPV VIS (http://www.immunize.org/vis/hpv.pdf) will be provided to the participant prior to administration of the vaccine. The vaccine will be administered as a 0.5 mL injection in the deltoid region of the upper arm or in the higher anterolateral area of the thigh. Participants will be monitored for adverse reactions to the vaccine for 30 minutes.

**Blood specimen**. A 28 mL blood specimen will be collected from each participant at the Pre-Transplant Vaccine Visits 1, 2, and 3, at the 6 Month and 12 Month Post-Transplant Visits, and (for participants who do not complete Pre-Transplant Vaccine Visit 2) before/at transplant surgery for measurement of the primary and secondary endpoints for the study. Ten mL of blood will be collected at the 13 Month Post-Transplant Visit to measure the anamnestic response to the booster vaccine dose by assessing HPV vaccine-type-specific titers. The primary biomarker of interest, HPV vaccine-type-specific seroconversion rates, will be measured in peripheral blood that will be drawn by routine venipuncture at the time of mandated blood draws, thus there will be no added risk to the participant.

Collection of cervical/vaginal and oral samples for HPV DNA testing. Cervical/vaginal and oral samples will be self-collected at the Pre-Transplant Vaccine Visits 1, 2, and 3, and at the 6 Month and 12 Month Post-Transplant Visits for HPV DNA testing. Cervical/vaginal samples will be self-collected using the Evalyn Brush® (Rovers Medical Devices B.V., Oss, Netherlands) for female participants only. Oral samples will be self-collected using a mouthwash gargle.

Collection of urine samples for HPV DNA testing. Urine samples will be self-collected at the Pre-Transplant Vaccine Visits 1, 2, and 3, and at the 6 Month and 12 Month Post-Transplant Visits from participants who consent to the collection of optional urine samples. Approximately 20-30 mL of urine will be self-collected at each visit in a sterile urine specimen container. Urine samples will be used for HPV DNA testing.

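### Adverse events are to be collected for 14 days after each dose, but participants without symptoms at the 24-72 hour call have no scheduled contact for the rest of that window

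*Combined protocol and SAP*

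**What the plan says.** The collection rule is in Section 11.1.1. It opens by requiring that "All AEs that occur after the informed consent is signed and baseline assessments are completed" be recorded. Item (a) says that unsolicited AEs, including local and systemic vaccine reactions, "will be collected for up to 14 days following vaccine administration", and names the first, second and third dose. Item (b) covers the time beyond day 14 and is narrower. Anticipated events and laboratory abnormalities that the site investigator or sponsor attributes to the renal disease, the transplant or the post-transplant regimens are no longer collected. Other AEs still are, and rejection or cancellation of a planned transplant is always reported as an SAE. Day 14 is thus the boundary between two recording rules.

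The contact schedule is elsewhere:

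- Section 7.7, on the day of dosing: "Participants will be monitored for adverse reactions to the vaccine for 30 minutes".
- Sections 5.7, 7.1 (footnote 15) and 7.3 (Telephone Calls): a call 24-72 hours after every dose. Section 7.3 explicitly includes post-transplant doses and Additional Study Visits, and says of the calls: "Participants will be asked if they have experienced any of the following symptoms to assess adverse events".
- The same sections: "If the participant reports adverse symptoms there will be a follow-up call on day" 7 ± 2, for the purpose of assessing resolution.
- Section 7.1: the row "Assess adverse events" is marked at Pre-Transplant Vaccine Visits 1, 2 and 3 and at the 12 Month Visit. It is blank at the 6 Month, 13 Month and Additional Study Visits.
- Section 3: "The 13 Month Post-Transplant Visit will include a blood draw only, and Additional Study Visits will only include administering the remaining vaccine doses". Sections 7.5 and 7.6 list no further procedures for these visits.
- Sections 7.6 and 8.4: participants not transplanted within 12 months go off-study once the Additional Study Visits and the follow-up calls are done.

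**The concern.** The rule and the schedule do not match. AEs are to be collected to day 14, but for a participant who is well when telephoned, nobody is scheduled to ask again within the window. The day 7 call does not close the gap, because it goes only to those who already reported symptoms and is meant to see whether these have resolved.

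The affected output is exploratory endpoint 3 (Sections 8.2 and 13.5), the vaccine safety profile by number of doses and by time from last dose to transplant. The events at risk are non-serious ones that start after the first call: they are the least likely to reach a medical record and the easiest to forget by the next visit. Onset also has to be placed on the right side of day 14, because the recording rule changes there, yet no contact is timed to establish it. Doses given after transplant, under immunosuppression, have the thinnest follow-up because no later visit is marked for AE assessment.

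**Working it through.** The plan gives no figure to reproduce. The check is a day count, with the dose on day 0 and the window taken as days 1-14.

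**Step 1. Does any visit fall inside the window?**

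| After | Next relevant visit | Timing | Inside days 1-14? |
|---|---|---|---|
| Dose 1, pre-transplant | Vaccine Visit 2 | at least 30 days (7.3); with the ± 2 weeks allowed in Section 3, 30 - 14 = day 16 at the earliest | No |
| Dose 2, pre-transplant | Vaccine Visit 3 | at least 3 months (7.3); the ± 2 weeks does not bring it near day 14 | No |
| Last pre-transplant dose | 6 Month Visit | 6 months ± 2 weeks after transplant (7.4) | No |
| Dose at the 12 Month Visit | 13 Month Visit | 1 month + 2 weeks later (7.5) | No |
| Dose at an Additional Study Visit | a second Additional Study Visit, or none | 3 months + 4 weeks later (7.6) | No |

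The transplant itself can fall within 14 days of dose 2 or 3, since the 30-day gap is required only for dose 1. Section 7.3.4 plans no research activity at surgery for those participants. The appointment reminder, 5-7 days before a visit, could reach day 9-11 if Visit 2 took place on day 16 (16 - 7 = 9; 16 - 5 = 11). Its stated purpose is to confirm the appointment, and it may be an automated message.

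**Step 2. Days with no scheduled contact.** Days left = 14 - day of last call.

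| Situation | Last call | Days left | Share of window |
|---|---|---|---|
| No symptoms, called at 72 hours | day 3 | 14 - 3 = 11 | 79% |
| No symptoms, called at 24 hours | day 1 | 14 - 1 = 13 | 93% |
| Symptoms, second call early | day 5 | 14 - 5 = 9 | 64% |
| Symptoms, second call on target | day 7 | 14 - 7 = 7 | 50% |
| Symptoms, second call late | day 9 | 14 - 9 = 5 | 36% |

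**Step 3. Post-transplant doses.** The three transplanted schedules in Section 3 contain 2 + 1 + 0 = 3 such doses: doses 2 and 3 in the one-dose schedule, dose 3 in the two-dose schedule, none in the three-dose schedule. All three have the 24-72 hour AE call. None is followed by a visit marked for AE assessment: the 13 Month Visit takes blood and the Additional Study Visit gives vaccine.

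**Step 4. Going off-study.** A participant without a transplant and without symptoms has completed the required calls by day 3 at the latest. Sections 7.6 and 8.4 then allow off-study status at least 14 - 3 = 11 days before the window closes.

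**The case against.** Item (a) speaks of unsolicited AEs. It can be read as stating which recording rule applies up to day 14, with no promise to contact participants throughout. This softens the conflict but does not remove it: every AE in the window must still be recorded, and the plan gives no scheduled way to learn of one that starts after the call.

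Two stronger conclusions are tempting.

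- A reader of the Schedule of Events alone might infer that post-transplant doses have no AE assessment at all. They do. Section 7.3 requires the AE call after these doses, the telephone row in 7.1 is marked at the 12 Month and Additional Study Visits, and the 30-minute observation applies.
- A reader might infer that the study is blind on days 4-14. It is not. There is the conditional call on day 7 ± 2, spontaneous reporting, the electronic record link (Section 11), SAE monitoring throughout (11.2.3) and rejection reported as an SAE at any time. The 6 Month Visit also includes history review and symptom assessment, though it may come many months after the dose.

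The share of days is not a share of reactions. Section 6.2 says the manufacturer solicited injection-site reactions and temperature for five days within its 14-day surveillance, so the documents do not show how many reactions start late. The endpoint is exploratory and descriptive, and only 24-28 evaluable participants are expected. All of this limits the size of the point. What stands is the lack of active questioning about late-onset, non-serious AEs.

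**Conclusion.** The 14-day window in 11.1.1(a) has no scheduled contact to match it. For participants without symptoms at the 24-72 hour call, 11 to 13 of the 14 days rest on passive capture or later recall, and after post-transplant doses no later visit is marked for AE assessment. Following the plan as written, late-onset, non-serious AEs are likely to be under-counted in exploratory endpoint 3. The documents do not allow the number missed to be estimated.

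This assumes that the calls are made as scheduled and that no diary or report card exists outside the text reviewed; none is described. SAE capture, rejection reporting and the primary seroconversion analysis are untouched. It is worth correcting because the remedy is cheap.

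**What to change.** 1. In Sections 5.7, 7.1 and 7.3, add one short AE call to every participant at about day 14 after each dose, whether or not symptoms were reported at 24-72 hours. In 7.6 and 8.4, state that nobody is closed off-study before that call.
2. In Sections 7.1 and 7.5, mark AE assessment at the existing 13 Month Visit and ask about events since the 12-month dose. This supplements the call and cannot replace it, because Appendix G makes the visit optional under the COVID-19 plan and no such visit follows an Additional Study Visit dose.
3. Do not shorten the window to 72 hours. That would move days 4-14 under item (b), where anticipated events attributed to renal disease or transplant are not collected, and so would reduce capture. If the call is not added, keep the window and report that active ascertainment ended at 72 hours for participants without symptoms.

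The cost is amendment wording, one extra short call per dose, and a few questions at a visit that already takes place.

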## b. AEs outside of the immediate post-vaccination periods (i.e., beyond 14 days):

- i. Anticipated clinically significant laboratory abnormalities, that in the view of either the Site Principal Investigator or the Sponsor, are related to the underlying renal disease, transplant procedure, or post-transplant regimens will not be collected or reported. (\*exceptions below)
- ii. Anticipated adverse events, that in the view of either the Site Principal Investigator or the Sponsor, are related to the underlying renal disease, transplant procedure, or post-transplant regimens *will not* be collected or reported. (\*exceptions below)

iii. All other adverse events will be collected and reported on AE CRFs. In situations where multiple AEs relate to a single unifying diagnosis, only the main unifying diagnosis should be reported as an AE on AE CRFs.

Example: In case of pneumonia with leukocytosis and chest pain that only requires outpatient treatment; the diagnosis of pneumonia should be reported as an AE, but leukocytosis and chest pain should not be reported as AEs.

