#### **5.6** Dose Modification

No dose modifications are planned. The study agent will be stopped in the event of an AE  $\geq$  grade 3 considered possibly, probably, or definitely related to the study agent. The second or third dose of Gardasil® 9 will not be administered to participants who experienced symptoms indicative of hypersensitivity after the first and/or second dose(s).

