#### 11.1.4 Assessment of relationship of AE to treatment

The possibility that the AE is related to study agent will be classified as one of the following: not related, unlikely, possible, probable, or definite.

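### Beyond 14 days after a dose, section 11.1.1(b) keeps anticipated, non-serious events with a suspected renal or transplant cause off the AE record, even when they are also considered possibly vaccine-related.

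*Combined protocol and SAP*

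**What the plan says.** Section 11.1.1 opens with a general duty: AEs after consent and baseline "must be recorded on the AE CRF (paper and/or electronic) whether or not related to study agent". It then sets caveats "For all unsolicited AEs not meeting the criteria for" serious adverse events.

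- **Item (a)**, up to 14 days after each dose: all unsolicited events are collected, anticipated or not.
- **Item (b)**, headed "AEs outside of the immediate post-vaccination periods (i.e., beyond 14 days": sub-item (i) removes anticipated clinically significant laboratory abnormalities and sub-item (ii) removes "Anticipated adverse events, that in the view of either the Site Principal Investigator or the Sponsor, are related to the underlying renal disease". Both sub-items name surgery and the drugs given after it as further grounds, and the consequence in (ii) reads "transplant procedure, or post-transplant regimens will not be collected or reported". Sub-item (iii) adds that "All other adverse events will be collected and reported on AE CRFs".
- **Exceptions to (b)**: events signifying allograft rejection, and events that cancel a planned transplant. Both are reported as SAEs.

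Section 11.1.2 lists severity grade and attribution to study agent among the data elements of a reported AE. Section 11.1.4 gives the attribution scale: "The possibility that the AE is related to study agent will be classified as one of the following", running from not related through unlikely, possible and probable to definite. Section 5.6 stops the study agent for an AE of grade 3 or higher "considered possibly, probably, or definitely related to the study agent", with no time limit. Exploratory endpoint 3 (sections 8.2 and 13.5) is the vaccine safety profile, summarized descriptively by number of doses and by time from last dose to transplant.

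**The concern.** The filter in (b) asks whether another cause is involved. It does not ask whether the vaccine can be ruled out. Both can be true of one event, and the possible category in 11.1.4 exists for such events. An event with dual or disputed attribution is nevertheless removed as soon as one party names the other cause.

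The trial has no comparator, so a missing event cannot show up as an imbalance between arms. The judgement that an event may be vaccine-related is then the main link between event and vaccine, and an event that is never collected carries neither grade nor attribution. Section 13.7 makes every participant evaluable for toxicity from the first dose, with no 14-day limit.

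The protocol itself gives a reason to want late events. The desensitization paragraph in section 2.3 raises immune activation and new HLA antibodies after vaccination as possible routes to graft injury. A laboratory change of that kind after day 14, short of rejection and not cancelling a transplant, could readily be called anticipated and transplant-related.

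**Working it through.** The plan gives no figure to reproduce. The check is a reading of the rule, followed by its overlap with section 5.6.

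**1. The rule as a condition.** For an unsolicited, non-serious event more than 14 days after a dose, let A mean related to renal disease, the transplant procedure or post-transplant regimens. Then

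excluded = anticipated AND (site investigator says A OR sponsor says A).

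Vaccine relatedness does not appear in the condition.

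**2. Applied to an anticipated, non-serious, late event outside the two exceptions:**

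| Site investigator | Sponsor | Result |
|---|---|---|
| Not A | Not A | Collected under (iii) |
| A | Possibly vaccine | Not collected |
| Possibly vaccine | A | Not collected |
| A and also possibly vaccine | Any view | Not collected |
| A only | A only | Not collected |

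The last row is the use for which the filter is plainly meant. The three rows above it lose an event that someone considers possibly vaccine-related. Item (iii) cannot restore them, because it covers only what (i) and (ii) have not already removed.

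**3. Direction of the effect.** The rule only removes events. The recorded number of late, possibly vaccine-related events can therefore equal or fall below the true number, never exceed it.

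**4. What stays outside the rule.** SAEs are outside the caveats and are reported under 11.2.2, apart from the planned transplant stay itself. Rejection and transplant cancellation are excepted. The introduction to section 11 says that data on post-transplant infections and rejection episodes are collected in any case. Unanticipated events stay in under (iii). What remains exposed is other anticipated, non-serious events and laboratory abnormalities after day 14.

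**5. Overlap with 5.6.** Grades 4 and 5 (life-threatening, fatal) are SAEs by the definition in 11.2.1, and the general grade 3 description in 11.1.3 includes hospitalization. The overlap is therefore mainly non-serious grade 3 events considered at least possibly related, in participants who still have a dose to come. Section 5.1 puts dose 2 at least 30 days after dose 1, so at least 30 − 14 = 16 filtered days precede it. Doses deferred until 12 months after transplant have a much longer filtered period before them. In that overlap 5.6 acts on an event that 11.1.1(b) says not to collect.

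**6. Calendar time, for context only.** Assume dose 1 falls 30 days before surgery for a one-dose participant, or 152 days (about 5 months) for a three-dose participant.

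- One dose, to month 12: 30 + 365 = 395 days; 14/395 = 3.5% unfiltered.
- Same participant, to 14 days after dose 3: 30 + 365 + 91 + 14 = 500 days; 3 × 14 = 42; 42/500 = 8.4%.
- Three doses before surgery, to month 12: 152 + 365 = 517 days; 42/517 = 8.1%.

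The filter therefore applies for 96.5%, 91.6% and 91.9% of these periods. These are shares of time and say nothing about how many events are lost.

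**The case against.** The case for the present text is substantial. Limiting late collection of expected transplant events is a deliberate choice for a licensed vaccine studied under an IND exemption, and section 11.1.1 introduces the caveats openly, so it does not contradict its own opening sentence. The most informative period, 14 days after every dose, is fully collected. Serious events, rejection, cancelled transplants and infections are covered. Endpoint 3 is exploratory and descriptive. All of this stands, and it limits the size of the point. It does not reach an event that fits the filter and is also considered possibly vaccine-related.

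A reader might infer more than the documents support:

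- *That one party can bar any non-serious event.* The event must also be anticipated, although that word is left undefined.
- *That 5.6 is left without input.* Section 5.6 turns on how an AE is considered and does not require an AE form. Medical history, symptoms and laboratory results are reviewed at vaccine visits 2 and 3 and at the 12-month visit, and section 8.3 separately allows a participant to stop the agent for an AE. An investigator could therefore still apply 5.6. What can be missing is the record.
- *That the filter formally precedes attribution.* Sections 11.1.1, 11.1.2 and 11.1.4 state no order. A sponsor overriding a site's rating also presupposes that the site has already told the sponsor of the event.
- *That more than nine tenths of the safety data are lost.* That figure is calendar time under an assumed schedule.

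**Conclusion.** The point holds within these limits. As written, 11.1.1(b)(i)-(ii) excludes late, anticipated, non-serious events and laboratory abnormalities on one party's attribution to renal disease, transplant or post-transplant regimens, whether or not the vaccine is also suspected. Any resulting bias in the descriptive safety profile runs one way, towards fewer possibly vaccine-related late events, and a single-arm design offers no comparison that would reveal it. For section 5.6 the consequence is mainly one of documentation: a non-serious grade 3 event could meet it and leave no record.

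The size cannot be given, because the documents contain no rate of late, anticipated, non-serious events and no share with dual or disputed attribution. The conclusion rests on reading the either/or wording literally and on the absence of any rule elsewhere for disagreement between site and sponsor. It is a cheap improvement to the collection rule and does not show that the safety data would be unusable.

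**What to change.** Add a third exception to 11.1.1(b): any AE or laboratory abnormality that the site investigator or the sponsor considers at least possibly related to Gardasil 9, on the 11.1.4 scale, is recorded on the AE CRF at any time after a dose, whatever other cause is also suspected. Grade and attribution would then be on file for these events. In the same edit, reconcile 11.1.1(b) with 5.6, so that no event on which 5.6 acts is one that 11.1.1(b) says not to collect. The content of 5.6 is a clinical matter on which this point takes no position.

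The cost is one sentence and a few more AE forms. The workload saving is kept for events that nobody links to the vaccine. Two further changes are not needed: requiring both parties to agree before an event is left out, and requiring formal attribution of every event before the filter applies. Either would add review of routine transplant events and give back much of that saving, and the third exception closes the gap without them.
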